10.4 Pharmacodynamic Assessment

10.4.1 Pharmacodynamic Analysis

The following PD parameters will be determined using noncompartmental methods in validated software program Phoenix WinNonlin (Certara, Version 8.3.5 or higher):

LY3872386 Part B – MAD

Parameter	Units	Definition
AUC	μg.h/mL	area under the concentration versus time curve
C_{max}	μg/mL	maximum observed concentration
t_{max}	h	time of maximum observed drug concentration

Part C -Multiple doses of Prednisone and Prednisolone:

CC

Parameter	Units	Definition
AUC	μg.h/mL	area under the concentration versus time curve
C_{max}	$\mu g/mL$	maximum observed drug concentration

 t_{max} h time of maximum observed drug concentration

tille of maximum observed drug concentrati

10.4.2 Pharmacodynamic Statistical Methodology

All derived PD concentrations CC

will be summarized by part and treatment, and listed. Plots

CONFIDENTIAL

Protocol Reference: J4L-MC-KMAA

will also be produced.

CCI

10.5 Pharmacokinetic/Pharmacodynamic Analyses

PK/PD modeling may be evaluated to characterize the exposure-response relationships between LY3872386 concentrations and various PD endpoints, provided the data are sufficient. This analysis, if performed, will be performed, and reported by Lilly.

10.6 Safety and Tolerability Assessments

10.6.1 Adverse events

Where changes in severity are recorded in the Case Report Form (CRF), each separate severity of the AE will be reported in the listings, only the most severe will be used in the summary tables. A pre-existing condition is defined as a condition that starts before the participant has provided written informed consent and is ongoing at consent. A non-treatment emergent AE is defined as an AE which starts after informed consent but prior to dosing. A TEAE is defined as an AE which occurs postdose or which is present prior to dosing and becomes more severe postdose.

All AEs will be listed. All TEAEs will be summarized by part, treatment, severity, and relationship to the study drug. The frequency (the number of AEs, the number of participants experiencing an AE and the percentage of participants experiencing an AE) of TEAEs will be summarized by part, treatment, Medical Dictionary for Regulatory Activities (MedDRA) (version is documented in the Data Management Plan [DMP]) system organ class and preferred term. The summary and frequency AE tables will be presented for all causalities and those considered related to the study drug by the investigator. Any SAEs will be listed by treatment group. For Parts B and C, AEs by day of onset will be presented, where onset time is based on the last dose received.

Discontinuations due to AEs will be listed.

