One cohort with 3 dose levels (CC) mg) is planned. A prednisone tablet is planned to be administered to healthy participants and taken PO on Day 1, followed by QD PO dose administration. The mg and mg prednisone groups' safety and PD data will be reviewed to determine if the 1 mg prednisone group will be conducted and/or if the dose may be altered. Participants in the mg and the mg (if conducted) groups will receive prednisone for a total of 30 days. Participants in the mg group will receive prednisone for a total of 7 days. Participants in all groups will be followed up for 2 weeks after the last dose of prednisone (Section 1.2). The mg and mg prednisone dose groups may occur in parallel with each other as well as in parallel to Part A SAD or Part B MAD.

- mg or mg dose levels
 - o PO QD dosing in healthy participants for a total of 30 days, then a 2-week follow-up period after each dose level
 - o Inpatient for approximately 30 days with follow-up period following the last dose of each dose level.
- mg dose level
 - o PO QD dosing in healthy participants for a total of 7 days, then a 2-week follow-up period
 - o Inpatient for approximately 7 days with follow-up period following the last dose.

Number of Participants:

participants (healthy participants and patients with AD) may be enrolled to ensure that CCl evaluable participants (CCl healthy participants and up to patients with AD) complete the study. Participants will include:

- healthy participants enrolled in Part A (SAD cohorts) on LY3872386
 - evaluable healthy participants
 - o replacements
- Up to patients with AD enrolled in Part B (MAD cohorts) on LY3872386
 - o Up to evaluable patients with AD)
 - o replacements
 - o Japanese patients are not intended to exceed more than approximately of the total evaluable patients with AD (for example up to approximately patients with AD)
- healthy participants enrolled in Part C (multiple dose cohort) on prednisone
 - o evaluable participants
 - o replacements

Ethical Considerations of Benefit/Risk: Not applicable

Data Monitoring Committee: No

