4.2. Scientific Rationale for Study Design

Study KMAA is the first-in-human dose study that will characterize the safety, tolerability, and PK of single doses of LY3872386 in healthy participants, multiple doses of LY3872386 in patients with AD, and multiple dose levels of prednisone in healthy participants. Participants receiving prednisone PO QD will not be blinded with a placebo. Blinding of subjects to prednisone was not deemed necessary as only objective safety and PD biomarker results following prednisone or LY3872386 administration will be compared. A lack of blinding would not be expected to affect these results. The data generated in this study will guide the design of the subsequent clinical trials.

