8.3.1. Timing and Mechanism for Collecting Events

This table describes the timing, deadlines, and mechanism for collecting events.

Event	Collection Start	Collection Stop	Timing for Reporting to Sponsor or Designee	Mechanism for Reporting	Back-up Method of Reporting
Adverse Event					
AE	Signing of ICF	Participation in study has ended	As soon as possible upon site awareness	AE CRF	NA
Serious Adverse	Event				
SAE and SAE updates – prior to start of study intervention and deemed reasonably possibly related to study procedures	Signing of ICF	Start of intervention	Within 24 hours of awareness	SAE CRF for mechanism of reporting and for back up SAE paper form	SAE CRF for mechanism of reporting and for back up SAE paper form
SAE and SAE updates – after start of study intervention	Start of intervention	Participation in study has ended	Within 24 hours of awareness	LSS SAE reporting process	NA
SAE* – after participant's study participation has ended and the investigator becomes aware	After participant's study participation has ended	NA	Promptly	SAE paper form	NA
Pregnancy					
Pregnancy in female participants and female partners of male participants	After the start of study intervention	Part A: 12 weeks after last dose. Part B: 14 weeks after last dose. Part C: 2 weeks after last dose.	Within 24 hours (see Section 8.3.2)	Pregnancy paper form	Pregnancy paper form
Product Compla		E 1 C . 1	W.1. 241 C	D 1 (C 11)	LATA
PC associated with an SAE or might have led to an SAE	Start of study intervention	End of study intervention	Within 24 hours of awareness	Product Complaint form	NA
PC not associated with an SAE	Start of study intervention	End of study intervention	Within 1 business day of awareness	Product Complaint form	NA
Updated PC information	_	_	As soon as possible upon site awareness	Originally completed Product	NA

				Complaint form	
				with all changes	
				signed and dated by	
				the investigator	
PC (if	Participation	NA	Promptly	Product Complaint	
investigator	in study has			form	
becomes aware)	ended				

Abbreviations: AE = adverse event; CRF = case report form; ICF = informed consent form; LSS = Lilly Safety System; NA = not applicable; PC = product complaint; SAE = serious adverse event.

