Participants will be required to return to the CRU for clinical assessments and blood samples on an outpatient basis (see protocol). The final follow-up visit will be approximately 12 weeks after the single dose of the study intervention in Part A, 14 weeks after the last dose of the study intervention in Part B, and 2 weeks after the last dose of prednisone in Part C.

Table 1: Summary of Participants in Cohorts Dosed with LY3872386

Part A: SA	Part A: SAD of LY3872386 in Healthy Participants ^a					
Cohort #	Planned Dose / Administration Route	Number of Planned Non-Japanese / Non- Chinese Participants	Number of Planned Japanese Participants	Number of Planned Chinese Participants	Total Number of Planned Completers	

CONFIDENTIAL Protocol Reference: J4L-MC-KMAA

		LY	PBO	LY	PBO	LY	PBO	
Cohort 1	mg IV							
Cohort 2	mg IV			I V. PDI	20			per cohort
Cohort 3	ccl mg IV		LY: PBO			per conort		
Cohort 5	mg SC							
Cohort 4 ^b	ccl mg IV	CCI						
Cohort 6 ^c	ccl mg IV	_	_	_	_	_	_	_
Cohort 7 ^c	ccl mg SC	CCI						per cohort
Cohort 8c	ccl mg IV	_	_	_	_			
Part B: MA	AD of LY 3872386 in I	Patients with	AD					
								Total
	Planned Dose /							Number of
Cohort #	Administration		Numb	er of Plann	ed Patien	its		Planned
	Route							Randomized
								Patients
Cohort 1	mg IV or SC			CCI				
Cohort 2	mg IV or SC							

Abbreviations: AD = atopic dermatitis; IV = intravenous; LY = LY3872386; MAD = multiple-ascending dose, PBO = placebo; PO = oral administration; SAD = single-ascending dose; SC = subcutaneous.

Table 2: Summary of Participants Dosed with Prednisone

Part C: Multiple Doses of Prednisone in Healthy Participants				
Dosing Group	Planned Dose / Administration Route	Total Number of Planned Completers		
Group 1	mg PO	CCI		
Group 2	mg PO	CCI		
Group 3	mg PO	COL		

Abbreviation: PO = oral administration

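### Part C adverse-event percentages compare a prednisone group observed for about 21 days with groups observed for about 44 days, and no common-window table is planned

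*SAP*

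**What the plan says.** The Protocol synopsis (1.1) gives Part C three prednisone dose levels of unequal duration. One "group will receive prednisone for a total of 7 days". The other two, one of them conditional, are covered by the statement that these "groups will receive prednisone for a total of 30 days". Follow-up is the same length for everyone: "Participants in all groups will be followed up for 2 weeks after the last dose of prednisone". SAP Section 5 agrees, placing the final visit "2 weeks after the last dose of prednisone in Part C".

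Protocol 8.3.1 sets the end of adverse-event collection at "Participation in study has ended", so the collection period is as long as each group's participation. SAP 10.6.1 puts no end on the window either: "A TEAE is defined as an AE which occurs postdose or which is present prior to dosing and becomes more severe postdose".

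The planned summary in SAP 10.6.1 is "The frequency (the number of AEs, the number of participants experiencing an AE and the percentage of participants experiencing an AE"), tabulated by part, treatment and MedDRA term. For Parts B and C it adds a display by onset day, with the day counted from the most recent dose. SAP Section 7 lists the three prednisone groups as consecutive table columns; the visible labels give drug, route and once-daily frequency, but no duration. Protocol 9.3.2 names event frequency as the primary endpoint for prednisone as well as for LY3872386.

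**The concern.** A crude percentage of participants with at least one event rises with the time over which events are counted. Where planned observation differs about twofold between adjacent columns, a reader cannot tell how much of a difference comes from the regimen and how much from the calendar.

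This matters for two reasons. These tables are the whole analysis of a primary endpoint, since no test or model stands behind them. The affected contrast is also one the study uses. The synopsis says that safety and PD data from two dose groups will decide whether the third is run or its dose changed. The conditional group is one of the two 30-day groups, so the pair reviewed is the 7-day group and the other 30-day group, which is the unequal pair. That review need not use the SAP tables, but crude percentages would mislead there in the same way.

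**Working it through.** The documents give no event rate for Part C and the group sizes are redacted, so there is no planned figure to reproduce. The check starts from the durations.

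**Observation time after first dose** (dosing days plus 14 days of follow-up, Protocol 1.1):
- 7-day group: 7 + 14 = 21 days
- 30-day groups: 30 + 14 = 44 days
- Ratio of observation: 44 / 21 = 2.10
- Ratio of time on drug: 30 / 7 = 4.29

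**Size of the artefact.** Assume the same constant hazard h per day in every group, on and off drug. Then P(at least one event by day T) = 1 − exp(−hT). The range of h is an assumption.

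| h per day | Crude, T = 21 | Crude, T = 44 | Days 1–7, any group |
|---|---|---|---|
| 0.005 | 10.0% | 19.7% | 3.4% |
| 0.01 | 18.9% | 35.6% | 6.8% |
| 0.02 | 34.3% | 58.5% | 13.1% |
| 0.03 | 46.7% | 73.3% | 18.9% |

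For h = 0.01: 1 − exp(−0.21) = 0.189; 1 − exp(−0.44) = 0.356; 1 − exp(−0.07) = 0.068. With no true difference in hazard, the crude columns differ by about 10 to 27 percentage points over this range. Expected events per participant differ by the full factor of 2.10 (0.21 versus 0.44 at h = 0.01). The Days 1–7 figure is the same in all groups.

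**When the artefact shrinks.** If events cluster after the first doses, the extra days add little. In the limit where none occurs after Day 7, the crude percentages are equal at equal early risk.

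**Does the onset-day display help?** With once-daily dosing the most recent dose is never more than about a day earlier while treatment continues, so almost every on-treatment event falls at about day 0 or 1. Neither time since first dose nor a common window can be read from it.

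**Would one rate per participant-day be enough?** Not by itself. On-drug time is 7/21 = 33% of observation in the short group and 30/44 = 68% in the long groups. If events arose only on drug, at equal daily hazard h, the rates would be 7h/21 = 0.33h and 30h/44 = 0.68h. That is a false ratio of about 2.05, so on-drug and off-drug time must be kept apart.

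**The case against.** The strongest reply is that duration is part of each prednisone regimen. The objective is to characterize safety in each dosing group, Part C is non-randomized, and Protocol 9.1 and SAP 10.6.15 rule out hypotheses and inferential safety analyses. On that view the crude percentage is an honest description of what happened over each planned course. This stands: the crude table is right for that purpose and should be kept. It does not show a reader how much of a difference between columns is due to time.

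It is also fair to say that the hazards above are assumed, that with group sizes redacted the gap cannot be set against sampling noise, and that one 30-day group may never be run. All events are listed, so a common window could be tabulated later, and supplementary analyses are allowed. The table shells and SAP 10.6.10 to 10.6.13 are not visible, so a relevant display there cannot be excluded, although adverse events are handled in 10.6.1. These points keep the matter small. Naming the window in advance still avoids choosing it after the events are known.

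Two stronger readings are tempting and are not supported:
- A reader might take Protocol 4.2 as a commitment to compare adverse-event percentages across prednisone doses. Its words are "only objective safety and PD biomarker results following prednisone or LY3872386 administration will be compared". That concerns objective results and a contrast between drugs, offered as the reason for not blinding prednisone. It does not plainly cover reported events across prednisone groups, and this point does not rest on it.
- A reader might infer that unequal observation could reverse a dose trend. Under the constant-hazard model, a rate in the 7-day group that is higher by any factor below 2.10 would show as a lower percentage. But the doses are redacted, so it is unknown whether that group has the highest, middle or lowest dose, and no trend analysis of Part C events is planned.

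**Conclusion.** The point holds as a minor matter of presentation for a primary endpoint. Planned observation of 21 versus 44 days follows directly from the protocol, and nothing in the visible text supplies a common window or a time denominator. The 7-day versus 30-day contrast is therefore partly a contrast of observation length; the two 30-day groups have equal planned time and are unaffected.

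The illustrative size, 19% versus 36%, rests on a constant hazard of 0.01 per day that is equal across groups and continues after dosing stops. Because no test is planned, no error rate, power or sample size is involved.

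**What to change.** Add three items to SAP 10.6.1 for Part C:
1. Beside the crude table, a table of treatment-emergent event incidence from first dose through Day 7, for every prednisone group. Days 1–7 is the period when all groups are scheduled to be on drug. A Day 1–21 window would set 14 off-drug days in the short group against on-drug days in the others.
2. Planned dosing days and observation days in the Part C column headings.
3. If rates are also given, on-treatment and post-treatment person-days and events reported separately, not as one pooled rate.

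The cost is one extra descriptive table from dosing dates and events already collected. The common window leaves out later events, including any after stopping, which is why the crude table stays. It does not remove differences due to non-random assignment, and it says nothing about the effect of longer dosing.

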10.6.2 Concomitant medication

Concomitant medication will be coded using the WHO drug dictionary (version is documented in the DMP). Concomitant medication will be listed.

CONFIDENTIAL Protocol Reference: J4L-MC-KMAA

10.6.4 Vital signs

Vital signs data will be summarized by part, treatment and time point together with changes from baseline, where baseline is defined as the Day 1 predose. Figures of mean vital signs and mean changes from baseline will be presented over time by treatment.

Values for individual participants will be listed.

10.6.5 Electrocardiogram (ECG)

For Part A, ECGs will be collected in triplicate at all time points excluding screening and the last scheduled follow-up visit. These ECG data will be presented as below. For Parts B and C, ECGs will be presented if collected in triplicate. Otherwise, ECGs from Parts B and C will not be presented, and any clinically significant findings from ECGs will be reported as an AE.

The ECG data will be obtained directly from the 12-lead ECG traces. These data include the PR, QT, QRS duration and heart rate. In addition, QT interval corrected using Fridericia's formula (QTcF) will be calculated as follows:

$$QTcF = \frac{QT}{\sqrt[3]{60/HR}}$$

The ECG data will be summarized by part, treatment and time point together with changes from baseline, where baseline is defined as the mean of the triplicate Day 1 predose. Figures of mean ECG data and mean changes from baseline will be presented by part and treatment. The frequency of participants with a maximum increase from baseline in QTcF interval will be summarized by part, and for each treatment according to the following categories: >30 ms and >60 ms. In addition, the frequency of participants with QTcF postdose values, according to the following categories: >450 ms, >480 ms and >500 ms, will be summarized by treatment.

CONFIDENTIAL Protocol Reference: J4L-MC-KMAA

Concentration-QTc Analysis (Part A only)

A plasma LY3872386 concentration-QTc analysis will be performed to assess the relationship between changes from baseline (mean of Day 1 predose assessments) in QTcF (Δ QTcF) and plasma LY3872386 concentrations across all treatments. IV and SC data will be pooled.

A linear mixed effects analysis model will be employed with ΔQTcF as the response variable, time-matched LY3872386 concentration as the explanatory variable (0 for PBO), centered baseline QTcF as an additional covariate, treatment (PBO=0 or LY3872386 =1), PK profile day, time (nominal time postdose), and the interaction between PK profile day and time as fixed effects, and a random intercept and concentration slope per participant. The model⁴ will have the form:

$$\Delta ECG_{i,j,k,l} = (\theta_0 + \eta_{0,i}) + \theta_1 TRT_j + (\theta_2 + \eta_{2,i})C_{i,j,k,l} + \theta_{3,k} DAY_k + \theta_{4,l} HOUR_l + \theta_{5,k,l} DAY_k \times HOUR_l + \theta_6 (ECG_{i,j,k=1,l=0} - \overline{ECG_{k=1,l=0}}) + \varepsilon_{i,j,k,l},$$

where $\Delta ECG_{i,j,k,l}$ is the change from baseline in QTcF parameter for participant i on treatment j (PBO, or LY3872386) on PK profile day k at l hours postdose. θ_0 is the population mean intercept in the absence of a treatment effect, $\eta_{0,i}$ is the random effect associated with the intercept term θ_0 , θ_1 is the fixed effect associated with the dichotomous treatment variable TRT_j , θ_2 is the population mean slope of the assumed linear association between concentration and ΔECG , $\eta_{2,i}$ is the random effect associated with the slope θ_2 , $C_{i,j,k,l}$ is the concentration for participant i on treatment j on PK profile day k at l hours postdose, $\theta_{3,k}$ is the fixed effect associated with categorical hours postdose l, $\theta_{5,k,l}$ is the fixed effect associated with the interaction term between PK profile day and hours postdose, θ_6 is the fixed effect associated with a participant's centered baseline QTcF value, $\overline{ECG_{k=1,l=0}}$ is the overall mean of $ECG_{i,j,k=1,l=0}$ (all participant's baseline QTcF parameter values, which are denoted as being on PK profile day 1 at hour postdose 0), and $\varepsilon_{i,j,k,l}$ is the residual error. It will be assumed the random effects are multivariate Gaussian distributed with mean vector $\mathbf{0}$ and an unstructured covariance matrix G, whereas the residuals, $\varepsilon_{i,j,k,l}$, are Gaussian distributed with mean 0 and variance r.

If this model fails to converge, the following covariance structures will be tested in order:

- Compound symmetry
- Variance components

The first covariance structure that converges will be used. If the model still fails to converge, the PK profile day-by-hour interaction term, followed by the random effects for slope, followed by intercept, will be removed until convergence is achieved. Other covariance structures may be considered if deemed appropriate.

The centered baseline QTcF will be derived as follows:

CONFIDENTIAL Protocol Reference: J4L-MC-KMAA

- Calculate the arithmetic mean of the triplicate QTcF parameter for each subject at each timepoint and use this in all subsequent calculations below.
- Calculate the overall baseline QTcF value, which is the mean of all participants' baseline QTcF values.
- For each participant, subtract the overall baseline QTcF value from their own individual baseline QTcF value. This will be each participant's centered baseline QTcF.

For postdose concentrations that are below the quantifiable lower limit of the assay (BQL), the following will be applied:

- For the PBO arm, all LY3872386 concentrations will be imputed as 0.
- For the LY3872386 arms, BQL concentrations will be treated as missing without any imputation.

The LY3872386 concentration slope and corresponding 90% CI will be reported. The model will also be used to derive the predicted $\Delta QTcF$ and PBO-corrected $\Delta QTcF$ ($\Delta\Delta QTcF$) at the geometric mean C_{max} of each dose level (PBO=0) for the last PK profile day along with the corresponding 90% CIs in a tabular format.

All $\Delta QTcF$ versus time matched LY3872386 concentrations will be plotted, with PBO concentration set to zero. A linear regression line from the model above will be included on the plot along with the corresponding 90% CI.

Predicted $\Delta\Delta QTcF$ from the above model versus LY3872386 concentration will also be plotted. The plot will include a linear regression line from the model above, corresponding 90% CI, and reference lines at the geometric mean C_{max} for each dose.

To check the model covariates are adequate, a scatter plot will be produced plotting the residuals of the fitted model versus LY3872386 concentration. A locally estimated scatterplot smoothing curve with 95% CI will be fitted to aid with this assessment.

The hysteresis loop plot between mean $\Delta\Delta QTcF$ and geometric mean LY3872386 concentration will be generated through 24 hours postdose in a temporal order for each PK profile day, with all LY3872386 doses combined. If deemed appropriate, further timepoints may be included if 24 hours does not adequately encapsulate the hysteresis loop. Mean $\Delta\Delta QTcF$ will be derived by performing a 2-sample t-test at each time point independently, with the 2 groups consisting of PBO and the combined LY3872386 treatments.

Similar analysis will be conducted for RR, HR, PR, and QRS.

CONFIDENTIAL Protocol Reference: J4L-MC-KMAA

Examples of the SAS code that will be used are as follows:

```
proc mixed data=xxx alpha=0.1;
  by param;
  class trt(ref='0') time subjid;
  model ΔECG = basec trt day hour day*hour conc / cl alpha=0.1 ddfm=kr2
residual;
  random intercept conc / subject=subjid type=un;
  estimate 'PBO' intercept 1 trt 0 1 conc 0/ cl alpha=0.1;
  estimate 'Δ at XX mg' intercept 1 trt 1 0 conc [cmax] / cl alpha=0.1;
  estimate 'ΔΔ at XX mg' trt 1 -1 conc [cmax] / cl alpha=0.1;
  ods output solutionF=sol;
  ods output estimates=estim;
run;
```

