7.1.3. Cardiovascular Stopping Criteria

7.1.3.1. QTc Stopping Criteria

If a clinically significant QTc finding is identified (including, but not limited to, changes from baseline in QTcF after enrollment), the investigator or qualified designee will determine if the participant can continue in the study and if any change in participant management is needed. This review of the ECG printed at the time of collection must be documented. Any new clinically relevant finding should be reported as an AE.

Discontinuation of IP should be considered by the investigator and the sponsor if any of the following occur in a participant:

- QTcF >500 msec
- increase from baseline in QTc >60 msec, from at least 2 consecutive readings

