8.2.3. Electrocardiograms

For each participant, ECGs should be collected according to the SoA (Section 1.3).

For Part A, a single ECG will be obtained at screening and at the last scheduled follow-up visit, but not transmitted to the central ECG vendor. At all other time points in Part A, consecutive ECGs are to be obtained in triplicate at approximately 1-min intervals. Additional tracings may be taken at each time point to obtain high quality data, when needed. Times are referenced to the end of dosing. ECGs will be obtained on Day 1 (predose [any time prior to dosing on the day of dosing but within approximately 90 minutes prior to the predose blood draw], end of infusion [approximately 6 hours after the end of infusion for the IV cohort and predose only for the SC cohort], Day 2 [approximately 24 hours after the end of dosing for both the IV and SC cohorts], and at any time on other specified visits [but prior to any blood draws at the same visit]).

For MAD Part B, a single ECG will be collected locally and stored at the investigator's site, unless the ECG values for participants in SAD Part A cohorts show clinically significant changes (for example, an increase in PR or QT interval). In this situation, triplicate 12-lead digital ECGs will be collected for participants in Part B cohorts.

For Part C, a single ECG will be collected prior to dosing locally and stored at the investigator's site unless the ECG values for participants show clinically significant changes (for example, an increase in PR or QT interval). In this situation, triplicate 12-lead digital ECGs will be collected for participants in Part C cohorts.

Any clinically significant findings from ECGs that result in a diagnosis and that occur after the subject receives the first dose of the study intervention should be reported to Lilly, or its designee, as an AE via eCRF.

When scheduled at the same time point, ECGs must be recorded before collecting any blood samples. Participants must be in a supine position for at least 5 minutes before ECG collection and remain supine but awake during ECG collection. Consecutive replicate ECGs will be obtained at approximately 1-minute intervals. ECGs may be obtained at additional times when deemed clinically necessary.

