9.3.5. Other Analyses

9.3.5.1. Other Safety Analyses

9.3.5.1.1. Clinical Laboratory Parameters, Vital Signs, and Electrocardiograms

Safety parameters that will be assessed include safety laboratory parameters, vital signs, and ECG parameters. The parameters will be listed and summarized using standard descriptive statistics.

Prior to any statistical analyses of the QT interval, QT values will be corrected for heart rate based on QTcF. The relationship between concentrations of LY3872386 and changes from

baseline QTcF will be explored to assess the effect of LY3872386 concentration on changes from baseline QTcF.

Additional analyses will be performed if warranted upon review of the data.

The baseline for safety parameters will be defined as the last evaluable value before the first dose.

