12. CHANGES FROM THE PROTOCOL SPECIFIED STATISTICAL ANALYSES

There were no changes from the protocol specified statistical analyses.

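### By default the SAP neither lists nor summarizes Part B and C ECGs, contrary to protocol 9.3.5.1.1 and without declaring the difference

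*SAP*

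**What the plan says.** **Analysis commitment.** Protocol 9.3.5.1.1 states: "Safety parameters that will be assessed include safety laboratory parameters, vital signs, and ECG parameters". It continues: "The parameters will be listed and summarized using standard descriptive statistics". Neither sentence is confined to Part A or to a number of replicates. The same section takes as baseline the most recent evaluable measurement preceding the first dose.

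**Collection.** Under protocol 8.2.3, Part A ECGs are triplicate except at screening and the final follow-up visit. For the patient part: "For MAD Part B, a single ECG will be collected locally and stored at the investigator's site". Part B changes to triplicate only if Part A shows clinically significant ECG changes. Part C has the same single-ECG default, with a switch if participants' ECG values show such changes.

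**Reporting.** SAP 10.6.5 states: "For Parts B and C, ECGs will be presented if collected in triplicate". The next sentence gives the default: without triplicates, "ECGs from Parts B and C will not be presented", and clinically significant findings appear as adverse events instead.

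**Declared differences.** SAP section 3 says the SAP takes precedence over the protocol's statistical considerations, and that substantial differences will be pointed out. SAP section 12 reads: "There were no changes from the protocol specified statistical analyses".

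**The concern.** The protocol promises ECG listings and summaries for the whole study. On the path the study expects to follow, the SAP delivers them for Part A only and does not record that as a change.

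This matters most in Part B, the only part in which LY3872386 is given repeatedly and the only one that gives it to patients with atopic dermatitis. By default, a reader of the study report would see Part B ECG information only where an investigator judged a finding clinically significant. There would be no values, no changes from baseline, no patients in the SAP's QTcF categories (increases >30 and >60 ms; values >450, >480 and >500 ms), and no numerical comparison with the randomized placebo group. A modest shift common to many patients, none of them individually remarkable, would leave no trace.

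**Working it through.** The plan gives no figure to reproduce, and no power or error-rate calculation applies. The check is a comparison of texts and a count of scheduled ECGs.

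**1. Provisions side by side**

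| Question | Protocol 9.3.5.1.1 | Protocol 8.2.3 | SAP 10.6.5 |
|---|---|---|---|
| Which parts? | No restriction | Part A triplicate; B and C single by default | Part A always; B and C only if triplicate |
| Listed? | Yes | Not addressed; B and C ECGs kept at site | Not in B and C by default |
| Summarized? | Yes | Not addressed | Not in B and C by default |
| Baseline | Last evaluable pre-dose value | Not addressed | Mean of the Day 1 predose triplicate |

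**2. The default branch.** Single ECGs are the rule in Parts B and C, and triplicates need a trigger. For Part B the stated trigger is a clinically significant change in Part A. A change first seen in Part B itself is not a stated trigger.

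**3. Whether another SAP provision rescues the data.** SAP 10.1 promises listings for whatever is in the database, but nothing visible says that single ECGs held at site are entered. If they are entered, 10.1 and 10.6.5 contradict each other. SAP 10.6.14 lists safety assessments not covered elsewhere in its section, but ECGs are covered. Neither provision restores the listing.

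**4. Whether an amendment explains the gap.** The SAP was written from the 01 September 2023 protocol. The change tables for amendments a and b show no change to 8.2.3 or 9.3.5.1.1, so the version difference is not the cause.

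**5. Scheduled Part B ECGs per patient** (early-discontinuation visit excluded)

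- First schedule (protocol 1.3.2.1): V1, V2 to V8, V804 = 1 + 7 + 1 = 9. Less V1 (screening) and V2 (predose, first dose): 9 − 2 = **7** post-baseline. These are V3 to V8 (6, all predose) and V804.
- Second schedule (protocol 1.3.2.2): V1, V2, V4, V6, V8, V805 = 6. Less V1 and V2: 6 − 2 = **4** post-baseline. These are V4, V6 and V8 (3, all predose) and V805.

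The last ECG in each count falls at the final follow-up visit, which protocol 4.1 puts about 14 weeks after the last dose. The on-treatment readings are therefore 6 and 3, all at trough.

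**6. Precision of single readings.** The documents give no within-participant QTcF variability. If replicate errors are independent with standard deviation σ, the mean of three has σ/√3, so this error component is √3 ≈ 1.73 times larger for a single reading. That calls for labelling, not omission: the SAP summarizes laboratory data and vital signs by part, treatment and time point with no replicate condition (10.6.3, 10.6.4).

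**The case against.** The best defence is that SAP 10.6.5 follows the specific collection plan in protocol 8.2.3, while 9.3.5.1.1 is a general sentence. The main QT evaluation sits in Part A, with triplicates, categorical QTcF summaries and a concentration-QTc model. The payload's hERG result (protocol 2.2) is reassuring. Part B's on-treatment ECGs are single and predose, so tables of them would say nothing about peak concentration. In a descriptive Phase 1 study without hypotheses, this could be called a matter of document alignment.

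Much of that stands. The tension does begin in the protocol, and Part A does carry the main QT assessment. But Part A is single-dose in healthy participants and cannot stand in for repeat dosing in patients. The general sentence remains a commitment, and section 12 of the SAP leaves the departure from it undeclared.

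Two stronger readings are tempting and are not supported:

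- *Repeat-dose QTc can never be tabulated.* The Part A trigger in protocol 8.2.3 would produce Part B triplicates, which SAP 10.6.5 would then present in full.
- *The QTc stopping criteria cannot work without a table.* Protocol 7.1.3.1 is applied at the bedside: the investigator reviews the printed ECG, documents the review and reports any new clinically relevant finding as an adverse event. One criterion is "increase from baseline in QTc >60 msec, from at least 2 consecutive readings", which a by-visit table of single scheduled ECGs could not reproduce anyway.

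**Conclusion.** The point holds for the default plan. With single ECGs, Part B and C readings are neither listed nor summarized, against the unrestricted wording of protocol 9.3.5.1.1, and the SAP does not declare the difference. The loss is 7 or 4 scheduled post-baseline ECGs per patient, according to the schedule used. These are the only repeat-dose LY3872386 ECG data.

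A reader might count 9 and 6 ECGs lost, but that includes screening and the predose reading before the first dose. A reader might also infer that the SAP discards analysis data already in hand. The documents show only that the ECGs are held at site; whether values reach the database is not stated.

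The conclusion assumes that the Part A trigger does not fire and that no redacted text provides for these ECGs. It should be corrected before reporting, but it does not threaten a primary endpoint. It matters less for Part C, which is open-label prednisone with no placebo comparison.

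**What to change.** Preferred change:

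- **Protocol 8.2.3:** provide for QT, heart rate, PR and QRS from each single Part B ECG to be entered on the CRF, and likewise in Part C for consistency.
- **SAP 10.6.5:** replace the non-presentation sentence with a provision along these lines: *Single ECGs from Parts B and C will be listed. Values, changes from baseline and the QTcF categories will be summarized by part, treatment and, where applicable, time point, and labelled as single readings (predose at Part B treatment visits).*
- **Baseline:** use the protocol 9.3.5.1.1 definition for these parts. Deleting the sentence alone would not be enough, because the SAP's ECG baseline is a triplicate mean that single recordings cannot supply.

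Minimum change, if the sponsor keeps the restriction: amend protocol 9.3.5.1.1 to say so, and declare the difference with its reason in SAP section 12.

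The preferred change costs entry of a few values per visit and a few more tables; no ECGs are added. Its drawback is that the tables show noisier readings not timed to peak concentration, which the labels should make plain. The minimum change costs only text, but leaves repeat-dose ECGs unreported by default.
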